## 1.6. Summary

We currently lack proven efficacious treatments for dermatomyositis-associated calcinosis. Preliminary reports in the literature and our personal clinical observations of positive outcomes following administration of sodium thiosulfate indicate the potential utility of sodium thiosulfate in dermatomyositis-associated calcinosis. Our clinical experience is supported by the plausible mechanisms of actions of this agent in the treatment of calcinosis. In addition, extensive off-label use and chronic use in studies evaluating sodium thiosulfate as a chemotherapy adjuvant have raised side effects that have been treatable and non-life threatening. More robust scientific evidence of the safety and efficacy of sodium thiosulfate as a treatment for calcinosis associated with JDM or DM is needed.

We therefore propose to conduct a clinical trial that will evaluate the efficacy and safety of sodium thiosulfate use in the treatment of calcinosis associated with dermatomyositis for juvenile and adult patients. There are several unique aspects of the proposed trial:

- This would be the first adequately-powered trial of any agent evaluating its efficacy in the treatment of calcinosis in JDM/DM.
- It would be one of few studies to evaluate a JDM/DM treatment in both adults and children.
- It will be designed to validate an assessment tool for calcinosis which is needed to promote research in this area.
- It will integrate a series of patient reported outcome measures allowing their utility in myositis and calcinosis to be assessed.
- It will allow the evaluation of novel imaging modalities in calcinosis to better understand not just the distribution of calcinosis, but also its activity.
- It will capture information about the natural history of calcinosis during the pretreatment phase, of which there is a dearth in the literature.
- It will assess a variety of proposed mechanisms of action of the drug in a multidimensional manner.

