Week 0 assessments may occur +/- 32 days and all assessments following it will be adjusted so that they start the appropriate number of weeks after week 0. **All assessments and contacts during the infusion period of Week 1 to Week 10, as described below, may occur in a window of +/- 4 days of the time point stated** (e.g., Week 6 may take place 6 weeks +/- 4 days after Week 0). **The Week 24 and Week 62 assessments may occur in a window +/- 14 days. The Week -4 assessments may occur in a window of +/- 10 days.**

Timing of study assessments and contacts from the study staff are as follows (see also Figure 1 for a study schematic):

- **Screening:** Participants will be screened over the phone prior to coming to the NIH Clinical Center for any study visits; section 9.1 outlines the procedures that will be followed to screen participants over phone and conduct the consenting process. Participants will sign a screening consent before any procedures are performed. Participants may come to NIH for an in-person screening evaluation. Interested individuals will provide access to their medical records for review prior to enrollment, and qualified study staff will discuss the potential participants' medical history with them to assess eligibility for the study. A Screening Evaluation Form will be completed for each potential participant; a copy of the form is attached as Appendix F, along with history and physical, laboratory studies and imaging studies as needed (Tables 4-8, found in Appendix B). Some of the blood and imaging testing may be performed at home prior to NIH screen. The main study consent will also be provided and reviewed with subjects at the time of screening evaluation.

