- **Week -10 (Enrollment/Intake):** Participants will come to the NIH Clinical Center for an initial evaluation to confirm qualification for the study and to conduct baseline evaluations. Study participants (or their parent(s)/guardian(s)) must sign a consent form, and minors must provide assent before they can be enrolled in the study and before any study assessments are performed. Any participants who are diagnosed with a medical condition or have laboratory abnormalities that were previously unknown will be notified and referred for medical care. For example, if a participant is found to be vitamin D deficient their physician will be notified and they can replace based on Institute of Medicine or National Osteoporosis Foundation guidelines. The Week -10 visit is expected to last up to approximately 7 days and may be done on either an inpatient or outpatient basis depending on the needs and mobility of the participant. Participants who have equivalent laboratory evaluations, imaging studies, or physical assessments within 1 week of their -10 visit may have those results used for this protocol instead of repeating those tests under this protocol.
- **Week -4:** Participants will complete questionnaires only (Calcinosis Assessment Tool, Mawdsley Calcinosis Questionnaire, Quality of Life, and patient-reported assessment measures); this may be done at the participant's home or at NIH.

**Abbreviated Title:** Sodium Thiosulfate (STIC)

**Version Date:** July 07, 2023

- **Week 0 (Baseline):** Eligible participants will return to the NIH approximately 10 weeks following the Week -10 visit for a second evaluation, during which time they will be admitted to the NIH Clinical Center as an inpatient and will initiate IV sodium thiosulfate (STS) therapy, dosed at 16 g/m^2 three times weekly for 10 weeks. Female individuals of reproductive potential must have a negative urine or serum pregnancy test prior to administration of sodium thiosulfate. Any participants experiencing intolerable side effects may discontinue therapy earlier. Participants who tolerate the therapy without an adverse event for 2 infusions and are deemed by the medical staff to be medically stable will be given the choice of becoming local outpatients to the NIH Clinical Center and returning 3 times weekly for infusions and evaluations during the 10-week sodium thiosulfate treatment period. Safety monitoring will be performed throughout the treatment period (see Table 8).

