#### 4. Inclusion and Exclusion Criteria

Participants will be enrolled without regard to gender, race, or ethnicity. Each potential participant must meet all of the following inclusion criteria in order to be eligible to enroll in the study:

- INCL 1. At least 7 years of age
- INCL 2. Meets Bohan and Peter criteria, as modified by the International Myositis Assessment and Clinical Studies Group (IMACS), (13,14, oddis) for probable or definite DM or JDM
- INCL 3. Has extensive calcinosis, defined as calcinosis involving at least 2 extremities or the torso
- INCL 4. Has moderate to severe calcinosis, defined as having a calcinosis activity visual analogue scale score of  $\geq 3.5$  cm out of 10 cm
- INCL 5. Is willing and able to comply with the requirements of the protocol and to undergo all testing
- INCL 6. Can have IV access established to receive study infusions
- INCL 7. Myositis disease activity is stable\*
- INCL 8. Medications for myositis are stable for at least 6 weeks prior to study entry\*\*
- INCL 9. Men and women of reproductive potential must agree to use a reliable form of birth control during the 62-week duration of the study
- INCL 10. Subjects or their legal guardian must sign a written informed consent

\*Stable myositis disease activity will be defined by physician global and patient/parent global VAS that are  $< 4$  cm (35), as well as creatine kinase (CK), lactate dehydrogenase (LDH), aldolase, aspartate aminotransferase (AST), and alanine aminotransferase (ALT) that are less than or equal to 2X upper limit of normal (ULN).

\*\*If a patient has a medication for myositis changed in this window for reasons besides their myositis activity and has returned to their baseline medication use prior to enrollment they will still be eligible.

A potential participant meeting any of the following exclusion criteria is not eligible to enroll in the study:

- EXCL 1. Is pregnant or breastfeeding
- EXCL 2. Has known allergies to sodium thiosulfate, any of its components, or dextrose

**Abbreviated Title:** Sodium Thiosulfate (STIC)

**Version Date:** July 07, 2023

- EXCL 3. Has severe myositis disease activity as defined by patient/parent or physician global activity visual analogue scale score >4 cm out of 10 cm

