## Appendix B. Time and Events Tables

**Table 4 Overview of Study Procedures Performed by Study Week**

	Pre-treatment			Treatment											Follow-up	
	Screening	Week												24	62	
		-10	-4	0	1	2	3	4	5	6	7	8	9			
Inclusion/exclusion criteria assessment	X	X														
Sodium thiosulfate treatment (3x/week) a,b					X	X	X	X	X	X	X	X	X			
Check for rapid responder and termination of treatment											X					
Medical history	X	X		X		X				X	X			X	X	X
Medication history and concomitant medications c	X	X		X		X				X				X	X	X
Review of systems every 2 weeks during infusion		X		X		X		X		X		X		X	X	X
Physical exam	X	X		X		X		X		X		X		X	X	X
Pregnancy test for women of child-bearing potential	X	X		X	X	X	X	X	X	X	X	X	X	X	X	X
Myositis clinical activity and damage assessments (Table 7)	X	X		X		X		X		X		X		X	X	X
Muscle function and strength testing (see Table 7 for details)	X	X		X		X		X		X		X		X	X	X
Skin Assessments (see Table 7 for details)	X	X		X		X		X		X		X		X	X	X
MRI (whole body)		X								X					X	X p
CT scan without contrast (all extremities)				X											X	X
CT scan without contrast (trunk)				X											X	X
MRI/PET				X q										X n,q		X m,q
Infrared photography		X		X		X				X				X	X	X
Nailfold capillaroscopy		X		X		X				X				X	X	X
Photography d		X		X						X				X	X	X
Laser Speckle Contrast Imaging	X		X		X					X				X	X	X

**Abbreviated Title:** Sodium Thiosulfate (STIC)

**Version Date:** July 07, 2023

	Pre-treatment				Treatment										Follow-up	
	Screening	Week														
		-10	-4	0	1	2	3	4	5	6	7	8	9	10	24	62
DEXA for safety monitoring and calcium scoring e	X o	X		X						X				X	X	X
Renal ultrasound		X		X l						X				X l	X	X l
Iothalamate clearance		X f		X						X				X	X g	X g
24-hour urine h		X		X						X				X	X	X
Blood collection (see Table 5 and Table 6 for details) i	X o	X		X	X	X	X	X	X	X	X	X	X	X	X	X
Calcinosis aspiration (as required, and if <15 cc)										X				X	X	X
Calcinosis aspiration (major)														X	X	X
Adverse event monitoring j		X	X	X	X	X	X	X	X	X	X	X	X	X	X	X
Questionnaire completion (see Table 7 below for details)	X	X	X	X		X		X		X		X		X	X	X
IV access k		X		X	X	X	X	X	X	X	X	X	X	X	X	X
Durometry		X		X						X				X	X	X

a. Subjects will receive once-weekly assessments between study weeks 0 and 10

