**Table 7 Schedule of Quality of Life and Myositis Assessments by Study Week**

Assessment	Completed By...	Screening	-10	-4	0	2	4	6	8	10	24	62
CHQ-PF50 (if pediatric) or SF-36 (if adult)	Patient AND Parent of participant (for CHQ); Participant (for SF-36)		X	X	X	X	X	X	X	X	X	X
Physician Calcinosis Visual Analogue Scale	MD	X	X		X	X	X	X	X	X	X	X
Calcinosis Type and Extent Form	MD	X(optional)	X		X			X		X	X	X
Calcinosis Sentinel Lesion Form	MD		X		X			X		X	X	X
IMACS Activity Core Set Measures:												
Physician Global Activity	MD	X	X		X	X	X	X	X	X	X	X
Patient/Parent Global Activity	Participant and parent of participant	X	X	X	X	X	X	X	X	X	X	X
CHAQ (if pediatric) or HAQ (if adult),	Parent of participant and pediatric participant (for CHAQ); Participant (for HAQ)	X	X	X	X	X	X	X	X	X	X	X
Childhood Myositis Assessment Scale (CMAS)	MD	X (optional)	X		X	X	X	X	X	X	X	X
Myositis Disease Activity Assessment Tool (MDAAT)	MD	X	X		X	X	X	X	X	X	X	X
IMACS Disease Damage Core Set Measures:												
Myositis Damage Index (MDI)	MD		X		X	X	X	X	X	X	X	X
Physician Global Assessment of Disease Damage	MD	X	X		X			X		X	X	X
Patient/Parent Global Assessment of Disease Damage	Participant and parent of participant		X	X	X			X		X	X	X

**Abbreviated Title:** Sodium Thiosulfate (STIC)

**Version Date:** July 07, 2023

Assessment	Completed By...	Screening	-10	-4	0	2	4	6	8	10	24	62
IMACS Assessment of Study Outcome Form	MD, Participant, and parent of participant			X a,b	X b			X		X	X	X
Disease Activity Score (DAS)	MD		X		X	X	X	X	X	X	X	X
Calcinosis Assessment Tool (CAT), including Pain VAS	Participant and parent of participant, reviewed by MD, MD	X	X	X a	X	X	X	X	X	X	X	X
Mawdsley Calcinosis Questionnaire	Participant and parent of participant, reviewed by MD, MD		X	X a	X	X	X	X	X	X	X	X
PROMIS® Questionnaire	Participant and parent of participant (pediatric pts)		X	X a	X	X	X	X	X	X	X	X
Skindex-29+3	Participant and parent of participant (pediatric pts)		X	X	X	X	X	X	X	X	X	X
Adult Myopathy Assessment Tool (AMAT)	Rehab Medicine Department		X		X			X		X	X	X
Motor Function Measurement (MFM)	Rehab Medicine Department		X		X			X		X	X	X
Functional Index 3 (FI3)	Rehab [name]		X		X	X	X	X	X	X	X	X
Passive Range of Motion (ROM)	Rehab Medicine Department		X									
Targeted Passive Range of Motion	Rehab Medicine Department				X	X	X	X	X	X	X	X

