9.	Does the potential participant have a calcinosis activity VAS score of $\geq 3.5$ cm (out of 10 cm)?	 Yes	 No	
10.	Is the potential participant able and willing to undergo all study procedures and assessments, including receiving IV infusions?	 Yes	 No	
11.	a. What is the patient/parent global disease activity VAS score for this potential participant? _____ b. What is the physician global disease activity VAS score for this potential participant? _____ c. Are the potential participant's lab values for CK, LDH, aldolase, AST, and ALT all $\leq 2X$ ULN?  Yes  No d. In consideration of (a), (b), and (c), does the potential participant have myositis disease activity that is stable (i.e., both VAS scores $< 4$ cm and all available lab values $\leq 2X$ ULN)?	 Yes	 No	
12.	If taking any medications for myositis, has this treatment been stable for at least 6 weeks prior to study entry? (If not taking medications for myositis, mark N/A in right-hand column.)	 Yes	 No	 N/A
13.	If of reproductive potential, is the potential participant willing to use a reliable form of birth control for the 62-week duration of the study? (If not of reproductive potential, mark N/A in right-hand column.)	 Yes	 No	 N/A
14.	Is the potential participant or the potential participant's parent/legal guardian able and willing to give consent for the study?	 Yes	 No	

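### If the 3.5 cm entry criterion is applied to the Week -10 VAS, regression to the mean enters the lead-in change and modestly understates the drug effect; the plan does not say which reading decides.

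*Combined protocol and SAP*

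**What the plan says.** **Entry criterion.** INCL 4 (Section 4) reads "Has moderate to severe calcinosis, defined as having a calcinosis activity visual analogue scale score of" 3.5 cm or more out of 10 cm. It names no visit.

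**Where it is checked.** The Table 4 row "Inclusion/exclusion criteria assessment" is ticked at Screening and Week -10, and not at Week 0. Section 3.1 says of the Week -10 visit: "Participants will come to the NIH Clinical Center for an initial evaluation to confirm qualification for the study and to conduct baseline evaluations". The footnotes to Figure 1 (Section 3.2) and Appendix D instead place the determination of eligibility at a screening visit before the study starts. Item 9 of the Screening Evaluation Form carries the test: "Does the potential participant have a calcinosis activity VAS score of" 3.5 cm or more.

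**Which readings exist.** The Table 7 row "Physician Calcinosis Visual Analogue Scale" is ticked at Screening, Week -10, Week 0 and later visits, so a separate screening score is scheduled. Attendance is optional, however: "Participants may come to NIH for an in-person screening evaluation". Section 3.1 also lets equivalent physical assessments made within one week of Week -10 stand in for the Week -10 ones.

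**How the score is used.** Sections 8.1 and 8.2 define the primary contrast as the lead-in change (Week 0 minus Week -10) minus the treatment change (Week 10 minus Week 0). Neither section mentions regression to the mean.

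**The concern.** A score that must exceed a cut-off is, on average, too high by part of its measurement error. If that score is also the start of the lead-in, the next reading tends to be lower even in stable disease. Week 0 and Week 10 carry no cut-off, so under independent errors nothing offsets the fall. The lead-in is the only comparator, so an artefactual improvement there is taken off the estimated drug effect.

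There is a smaller second consequence. Section 1.6 says of the trial: "It will capture information about the natural history of calcinosis during the pretreatment phase, of which there is a dearth in the literature". A selection artefact would appear in the VAS part of that description as slight spontaneous improvement.

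**Working it through.** **Reproducing the plan's figure.** Inputs from Section 8.2: two-sided paired t-test, alpha 0.05, SD of the contrast 10 mm, true difference 10 mm. Noncentral t power is 88.3% at n = 12 and 91.1% at n = 13, so the stated 13 is reproduced. With the 25% dropout of Section 8.3, 13/0.75 = 17.3, which rounds up to the stated 18.

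**Direction.** D = (W0 - W-10) - (W10 - W0) = 2·W0 - W-10 - W10, and a positive D means benefit. If selection raises the expected error in W-10 by b, the expected D falls by b.

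**Size.** The documents give no VAS distribution and no retest error, so these are assumptions:
- Normal true scores with pre-selection mean m = 35, 45 or 55 mm and between-patient SD s = 10, 15 or 20 mm.
- Independent normal errors that account for all of the SD of D. Then Var(D) = (4 + 1 + 1)·se², so se = SD/√6. That is 4.08 mm at SD 10 and 6.12 mm at SD 15.
- SD of D held at the protocol's value after selection.

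With Week -10 as the sole gate, b = (se²/sX)·φ(a)/(1 - Φ(a)), where sX² = s² + se² and a = (35 - m)/sX.

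*Largest case at SD 10 (m = 35, s = 10):* sX = √(100 + 16.67) = 10.80 and a = 0, so b = (16.67/10.80) × (0.399/0.5) = 1.23 mm. Power at 10 - 1.23 = 8.77 mm is 82.7%, and 16 completers would be needed for 90%.

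*Smallest case (m = 55, s = 10):* a = -20/10.80 = -1.85, so b = 1.54 × 0.074 = 0.11 mm. Power is about 90%.

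The two-gate rows come from simulation, with Screening and Week -10 both required to reach 35 mm and errors independent.

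| Gate | SD of D and true effect | Bias, mm | Power, n = 13 |
|---|---|---|---|
| None, or separate screening reading only | 10 and 10 | 0 | 91% |
| Week -10 only | 10 and 10 | 0.1 to 1.2 | 83% to 90% |
| Screening and Week -10 | 10 and 10 | 0.1 to 0.75 | 86% to 91% |
| Week -10 only | 15 and 15 | 0.3 to 2.6 | 78% to 90% |

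**Effect on false claims.** With no drug effect, SD 10 and a 1 mm bias, the chance of wrongly declaring benefit falls from 2.5% to 1.1%.

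**If correlation decays with time.** Suppose the correlation is r over 10 weeks and r² over 20. Regression then continues from Week 0 to Week 10 and partly cancels: b = (1 - r)²·λ instead of (1 - r)·λ, where λ is the mean excess of the selected Week -10 scores. With m = 35 and a total VAS SD of 20, λ = 20 × 0.798 = 15.96. For r = 0.9, 0.8 and 0.7, b is 0.16, 0.64 and 1.44 mm, against 1.60, 3.19 and 4.79 mm without decay.

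**The case against.** The best reply is that the documents never say a patient scoring below 3.5 cm at Week -10 is turned away. Two footnotes place eligibility at screening, the cut-off sits on the screening form, and Table 7 schedules the screening VAS without the optional tag it gives some other screening items. Where Week -10 eligibility checks are spelled out, they concern bone density and calcinosis extent on DEXA (Section 3.4) and pregnancy (Section 5.5). If screening alone decides, the bias is zero under independent errors.

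That reply turns the point into an ambiguity but does not remove it. Section 3.1 and Table 4 make Week -10 an eligibility check without exempting INCL 4. In-person screening is optional, and the VAS weighs warmth, texture and consistency (Section 5.4), which are hard to judge by telephone. The one-week reuse clause can be read as letting one score fill both roles.

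A reader might infer a much larger loss. With a VAS SD of 20 mm, a mean of 35 mm and correlations of 0.9, 0.8 and 0.7, the artefact of 1.6, 3.2 or 4.8 mm combined with a contrast SD of 10 would put power at 79%, 62% or 41%. The documents do not support this, because the inputs conflict. Under equal correlations the SD of D is 20·√(6(1 - r)), which is 15.5, 21.9 or 26.8 mm and not 10. At those values power for 10 mm is already about 57%, 33% or 24% with no artefact. That calculation also ignores the screening score and any regression after Week 0. A pre-selection mean of 35 mm implies that half of those arriving at Week -10 fail the cut-off, which is unlikely after a screening score at the same level.

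Upward scoring near the cut-off by an unblinded physician is possible, but its size is unknown. The same open-label scoring at Week 10 could favour the drug.

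**Conclusion.** The point holds as a conditional one. The plan leaves open whether the Week -10 VAS decides INCL 4. If it does, the primary contrast is biased toward no effect. At the protocol's planning case the cost is at most about 8 points of power with Week -10 as the sole gate (91% to 83%) and about 5 with both gates (91% to 86%). It is close to nothing if most referred patients score well above 35 mm. These figures rest on the assumed means and SDs and on independent errors, and decaying correlation would make them smaller.

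The bias does not create a false claim of benefit. It should not be set against the statement in Section 1 that spontaneous resolution is rare, since a shift of a millimetre or so in mean VAS is a different quantity. The lead-in imaging and questionnaires have no VAS cut-off. The case for acting is that the bias sits in the only control, that 13 completers leave little margin above 90%, and that the remedy is nearly free.

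**What to change.** In Section 4 and in a note to Table 4, state three things:
1. INCL 4 is decided on a physician-scored screening VAS, already scheduled in Table 7 and distinct from the Week -10 VAS.
2. The Week -10 VAS is a baseline measurement, and a value below 3.5 cm there does not by itself remove the patient.
3. The one-week reuse clause in Section 3.1 does not allow one VAS reading to serve as both the qualifying and the Week -10 value.

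In Section 8.1, add that patients without a separate in-person screening VAS are flagged and that the primary contrast is repeated without them as a sensitivity analysis.

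The cost is a few sentences, with no new visit or measurement for patients screened in person. The downside is that a few patients slightly under 3.5 cm at Week -10 stay in.

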- EXCL 4. Has had an escalation of immunosuppressive therapy in the 2 months prior to enrollment for the purpose of treating active myositis disease activity, including the addition of a new agent to treat the patients underlying disease or an increase in dose of an existing medication used to treat the patient's disease (other than an adjustment for weight or body surface area in children)
- EXCL 5. Has a malignancy or had a malignancy within 5 years of diagnosis of their DM (except for benign skin lesions or basal cell carcinoma)
- EXCL 6. Known or suspected history of alcohol or drug abuse in the 6 months prior to study enrollment
- EXCL 7. Has systemic lupus erythematosus, scleroderma, or a condition other than DM that is associated with calcinosis as a complication
- EXCL 8. Has had a change in medications used specifically for calcinosis in the 2 months prior to enrollment, including but not limited to alendronate, etidronate, pamidronate, probenecid, colchicine, diltiazem, thalidomide, and aluminum hydroxide
- EXCL 9. Has used probenecid, diltiazem, aluminum hydroxide, or hydrochlorothiazide in the 2 months prior to enrollment
- EXCL 10. Has currently or has a history of any of the following: heart failure, renal impairment (GFR less than 30 representing severe renal disease), liver disease (Child-Pugh class C), arrhythmias (that are symptomatic or are concerning for progression to symptomatic arrhythmias), or recurrent kidney stones (more than one episode of symptomatic kidney stones separated by at least 1 month), or QT prolongation, or hypocalcemia, or metabolic acidosis, or hypotension
- EXCL 11. Has severe osteoporosis or has had a bone fracture within a year prior to enrollment. For adults, severe osteoporosis as defined by the World Health Organization (WHO) as bone mineral density (BMD) 2.5 standard deviations below that of a young, normal adult (T-score at or below -2.5 and one or more fractures). For individuals, less than age 18, severe osteoporosis as defined by the First Pediatric Consensus Development Conference as a Z-score below -2 and one or more fractures.
- EXCL 12. Has a psychiatric illness or medical non-compliance that the study team feels will make the patient unlikely to complete the study
- EXCL 13. Has dysphagia where non-oral feeding alternatives are needed.
- EXCL 14. Requires supplemental oxygen therapy

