b. Sodium thiosulfate treatments are administered 3 times/week, starting at Week 0 and continuing through Week 10

c. At Week -10, Week 0, Week 24, and Week 62, medication history and concomitant medications will be reviewed with the subject in detail; at all other visits, any changes occurring since the last evaluation will be assessed.

d. Photography will be performed more frequently than indicated if there's a noted change

e. If a DEXA scan has been performed within 6 months prior to initiation of the study, that will be used as the baseline DEXA evaluation

f. Iothalamate clearance not performed for children at Week -10 visit

g. Iothalamate clearance is optional at Week 24 and Week 62 if normal previously

h. Urine assessment will include calcium, phosphorus, pyrophosphate, creatinine, citrate, and urate; while receiving sodium thiosulfate infusions, evaluations for renal function and urinary excretion of calcium will be performed weekly. They will use a split collection with Cr, Na, CA, Mg, P, and urate coming from the non-acidified container. Cr, citrate, and oxalate will be collected from the acidified container.

i. While receiving sodium thiosulfate infusions, evaluations for renal function, metabolic acidosis, PT/PTT, and serum calcium will be performed weekly

**Abbreviated Title:** Sodium Thiosulfate (STIC)

**Version Date:** July 07, 2023

	Pre-treatment				Treatment										Follow-up	
	Week															
	Screening	-10	-4	0	1	2	3	4	5	6	7	8	9	10	24	62
j.	These are the times for formal review for adverse events. In addition, patients, will have contact information to reach the study team to contact them for any expected adverse events they experience at other times.															
k.	If needed, a PICC or Port-A-Cath line will be inserted to maintain IV access for multiple infusions and this may occur prior to a scheduled visit.															
l.	Only performed if the CT scan during that visit does not include the kidneys.															
m.	If a patient has become pregnant or is breastfeeding and is unable to receive a MRI/PET at this visit they will instead receive a whole body MRI.															
n.	At week 10 adults patients will receive a MRI/PET while pediatric patients will receive a whole body MRI instead.															
o.	May be performed by their home physician															
p.	If the MRI/PET is not performed at this point a whole body MRI if safe will be performed instead.															

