9.	Has the potential participant taken any of the following medications in the past 2 months:  • Probenecid; • Diltiazem; • Aluminum hydroxide; • Hydrochlorothiazide?	 Yes	 No	

	Does the potential participant have current or a history of any of the following: 
 
• Heart failure;
 
• Renal impairment (GFR less than 30 representing severe renal disease);
 
• Liver disease (Child-Pugh class C);
 
• Arrhythmias (that are symptomatic or are concerning for progression to symptomatic arrhythmias);
 
• Recurrent kidney stones (more than one episode of symptomatic kidney stones separated by at least 1 month)?
 
	 Yes	 No	
10.	a. If $\geq 18$ years of age, does the potential participant have a T-score at or below -2.5 and one or more fractures?  ● Yes ● No	 Yes	 No	
11.	b. If $<18$ years of age, does the potential participant have a Z-score below -2 and one or more fractures?  ● Yes ● No	 Yes	 No	
	c. In consideration of (a) or (b), does the potential participant have severe osteoporosis (A yes for either answer above) or has he/she had a bone fracture in the past year?			
12.	a. Does the participant have a psychiatric illness or a history of medical noncompliance?  ● Yes ● No (mark N/A in right-hand column)	 Yes	 No	 N/A
	b. In consideration of (a), if yes, does the study team feel this will make the patient unlikely to complete the study?			
13.	a. Does the potential participant have dysphagia?  ● Yes ● No (mark N/A in right-hand column)	 Yes	 No	 N/A
	b. In consideration of (a), if yes, is it to a severity where non-oral feeding alternatives are needed to maintain adequate nutrition?			
14.	Does the potential participant require supplemental oxygen?	 Yes	 No	
15.	Has the potential participant experienced $>3$ episodes of cellulitis requiring IV antibiotics related to calcinosis within a year prior to enrollment, or had cellulitis within the prior month?	 Yes	 No	
16.	Has the potential participant ever taken sodium thiosulfate (previously or currently receiving)?	 Yes	 No	

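### Eligibility is last formally assessed 38 to 102 days before dosing, no supplied rule makes the Week 0 GFR, calcium or acid-base results a condition of the first infusion, and the Appendix F form omits four EXCL 10 conditions

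*Combined protocol and SAP*

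**What the plan says.** **Timing.** Section 3.1 gives Week -10 the task of confirming that a participant qualifies, then says that "Eligible participants will return to the NIH approximately 10 weeks following the Week -10 visit for a second evaluation". At that return visit the participant is admitted and treatment begins. The visit window is wide: "Week 0 assessments may occur +/- 32 days". In Appendix B, Table 4, the row "Inclusion/exclusion criteria assessment" is marked at Screening and Week -10 and nowhere else. Footnote b of that table fixes the start of dosing: "Sodium thiosulfate treatments are administered 3 times/week, starting at Week 0 and continuing through Week 10". Section 3.1 also allows reuse of earlier tests: participants with equivalent results "within 1 week of their -10 visit may have those results used for this protocol instead of repeating those tests".

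**Criteria.** EXCL 10 in Section 4 applies to current or past conditions. It includes "renal impairment (GFR less than 30 representing severe renal disease" and closes with "or QT prolongation, or hypocalcemia, or metabolic acidosis, or hypotension".

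**Form.** Exclusion item 10 of the Appendix F screening form is the counterpart of EXCL 10. Its list stops at "Recurrent kidney stones (more than one episode of symptomatic kidney stones separated by at least 1 month". The form's Eligibility Determination then makes a participant eligible when the applicable inclusion answers are yes and the applicable exclusion answers are no.

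**Week 0 tests.** Tables 5 and 6 schedule chemistry with cystatin C, the mineral panel, ionized calcium and venous blood gas at Week 0 for adults and children. Section 5.15 adds iothalamate clearance.

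**The concern.** A participant can qualify at Week -10, develop reduced renal function, hypocalcemia or acidosis during the lead-in, and reach the first infusion with an abnormal result on file that no written rule requires anyone to act on. The only visit in between, Week -4, consists of questionnaires and may be completed at home.

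The plan itself explains why these three criteria matter. Section 10.1.2.1 says that toxicity may be greater when the kidneys are impaired, and Section 5.15 says that reduced renal function could prolong exposure considerably. Section 10.1.2.1 also reports calcium disturbances in the team's own experience, and Section 14.3 describes acidosis that could build up over repeated infusions.

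The form is a separate weakness. If it is followed as written, a person whom Section 4 excludes for any of the four omitted conditions can pass item 10.

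**Working it through.** **1. Interval from last formal check to dosing.** Inputs from Section 3.1: nominal gap of 10 weeks; Week 0 window of plus or minus 32 days.

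- Nominal: 10 × 7 = 70 days
- Shortest: 70 - 32 = 38 days (38/7 = 5.4 weeks)
- Longest: 70 + 32 = 102 days (102/7 = 14.6 weeks)
- Oldest reusable Week -10 result: 102 + 7 = 109 days

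Venous blood gas and ionized calcium are not marked at Week -10 in Tables 5 and 6. For those two tests the formal check rests on Screening, and the table footnotes let Screening tests be done by an outside physician. The chemistry and mineral panels are drawn at Week -10.

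**2. Rules that could stop or delay the first infusion.**

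| Item | Rule in the supplied text | Where |
|---|---|---|
| Pregnancy | Negative test required before drug | 3.1, 5.5 |
| Fracture before Week 0 | Wait a year or more, then a second Week -10 visit | 12.2, 14.2 |
| Hemoglobin below 9 | Pause pending hematology input | 14.2 |
| Hyperglycemia, grade 3 or higher | Pause | 14.2 |
| Week 0 CT | Possible reassessment of risk and benefit; concerns calcinosis and surgery | 5.8 |
| GFR | Purpose of the Week 0 test stated; no threshold for holding drug | 5.15 |
| Calcium | Corrective action as needed. Pre-infusion checks in the first two adults and one child; abnormalities go to the DSMB to decide on further monitoring | 10.1.2.1, 3.1 |
| Acid-base | Weekly monitoring over Weeks 0 to 10; no hold rule | 14.3, Table 8 |
| Any new medical problem | Withdrawal if judged unsafe to continue | 14.2 |

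The withdrawal rule in Section 14.2 for grade 3 or higher events applies to events thought to be related to study drug, so it cannot act before the first dose. The last four rows leave GFR, calcium and acid-base to judgement at Week 0.

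**3. EXCL 10 against Appendix F item 10.**

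- In both (5): heart failure, renal impairment, liver disease, arrhythmias, recurrent kidney stones.
- In Section 4 only (4): QT prolongation, hypocalcemia, metabolic acidosis, hypotension.
- Total in Section 4: 5 + 4 = 9.

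Hypocalcemia and metabolic acidosis, two of the three criteria at issue at Week 0, are therefore not itemized on the form either.

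**The case against.** The strongest reply is that starting drug at Week 0 is already a supervised clinical decision. Participants begin as inpatients. History is updated, the physical exam repeated and medications reviewed. Section 5.8 treats Week 0 as the moment of deciding on medical therapy, Section 10.1.2.1 promises correction of electrolyte disturbances, and Section 14.2 lets clinicians withdraw anyone who develops a problem. All of this stands, and it limits the point to the absence of a written condition. A reader might infer that participants are dosed without any check at Week 0. The documents do not support that.

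A reader might also take two cited hazards as first-dose harms. The acidosis in Section 14.3 is described as accumulating over several infusions, and on-treatment monitoring addresses it. The QT prolongation in Table 2 occurred in a trial in hemodialysis patients and resolved when the dialysate calcium was raised. Neither shows what an undetected abnormality would do at a first infusion. Of the three, renal function bears most directly on it.

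A third tempting reading is that children have no GFR before dosing. They have no iothalamate clearance before Week 0, but EXCL 10 does not ask for a measured GFR, and chemistry with cystatin C is drawn in children at Screening, Week -10 and Week 0.

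On the form, item 19 asks about any condition that significantly raises the risk, Section VIII requires a signed statement that all entry criteria are met with no exclusions, and Section 4 itself lists all nine conditions. These lower the chance of a wrong enrollment. They cover the omission only in part, because item 19 asks for an opinion about risk, whereas EXCL 10 excludes the conditions outright.

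Finally, EXCL 9 and EXCL 15 look back from enrollment, which might suggest new pre-dose rules for those drugs and for cellulitis, or a compulsory repeat of the Week 0 VAS if dosing slips. The case for these is weak: the documents name no thiosulfate-specific hazard for recent cellulitis, Section 4.1 already aims to keep medications stable, and the VAS anchors the primary outcome, so changing it calls for its own justification.

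**Conclusion.** The point holds and is minor. The last scheduled eligibility assessment is 38 to 102 days before dosing, and no supplied rule applies the GFR, hypocalcemia or metabolic acidosis criteria to the Week 0 results before the first infusion, although the tests are already scheduled. Separately, the Appendix F form omits 4 of the 9 EXCL 10 conditions while its answers determine eligibility.

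This rests on the supplied text alone. The Manual of Procedures cited in Section 5.3 was not supplied and could contain a dosing-hold rule. The documents give no rate of new abnormalities during the lead-in, so no number of affected participants can be stated. Nor do they show that anyone excluded by Section 4 has been, or would be, dosed.

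**What to change.** 1. Add QT prolongation, hypocalcemia, metabolic acidosis and hypotension to Appendix F exclusion item 10.
2. Mark Week 0 in the Table 4 eligibility row. In Section 3.1, require investigator sign-off before the first infusion that the current Week 0 GFR, based on chemistry and cystatin C, is not below 30, and that calcium and blood gas, judged against the laboratory's reference limits, show no uncorrected hypocalcemia or metabolic acidosis.
3. Do not wait for iothalamate, which can need a 24-hour sample and may be skipped for logistical reasons. If it later shows GFR below 30, hold the next infusion.
4. Apply current values, so that a transient abnormality that has been corrected defers dosing and does not bar it.

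If the Manual of Procedures already holds such a rule, a reference in Section 3.1 would replace items 2 to 4.

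The cost is a small amendment and a short checklist using tests already scheduled. There will be a short wait for results (turnaround is not stated) and an occasional deferral. The window leaves 102 - 70 = 32 days beyond nominal Week 0. A participant who is never dosed uses one of the 18 - 13 = 5 places above the completer target.
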